Adolescent Health Club Component and Evaluation: Households with AGYW ages 15 to 25 will be identified by community health workers from randomly selected block sectors of the study area. Clubs will be conducted in separate neighborhood sectors, to limit contamination. Conducting club meetings near to the lanes adolescent girls live in will make it easier for them to attend. To further assess and address potential contamination, we will ask individuals to verify the adolescent health club they attended in the post-intervention survey, whether they attended an additional health club outside our intervention (such as, in school). If any contamination is evident based on this question, then we will model it. AGYW and their mothers (if unmarried and under the age of 18) will be approached by a member of the research team and the adolescent health club intervention will be explained. If consent is obtained, the AGYW will be enrolled, and randomized to either participate or join the wait-list. AGYW will complete the pre-intervention evaluation instrument upon enrollment. In addition to the activities in the "It's All One" Curriculum spread over eight modules, providers from the sensitization component will attend one meeting to discuss services available in the adolescent-friendly clinics, and hear young women's previous experiences accessing care. Similar to the process for the provider sensitization component, the facilitator will complete a log after each session to code activities as implemented fully, implemented partially or modified significantly and describe any changes. The log will also include a section to document any unusual events associated with any of the sessions, and the effect of these events on implementation, acceptability, or feasibility. Every other session will be observed and documented in fieldnotes that will be analyzed to contribute to process evaluation (see analysis details below). As with the provider component, the log and fieldnotes will enable a qualitative assessment of intervention fidelity. When young women complete the curriculum, they will also complete the post-intervention evaluation instrument. A sub-sample of young women (N=15) will be asked to participate in a focus group discussion to reflect on the club's impact and acceptability. Domains measured by previously validated instruments^(32, 48, 66, 123-126) to be covered in the pre- and post-intervention surveys are shown in Table 3. There are relatively few validated quantitative measures of implementation outcomes,^(127, 128) and none in Hindi, thus the measure we have chosen⁽¹²⁹⁾ will have to be translated and back-translated to ensure comprehension.

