
Table 1: Domains to be covered in AGYW pre- and post-intervention surveys.

Pre-Intervention Survey Domains	Post-Intervention Survey Domains

Demographics	Demographics
Clinic service uptake/use	Clinic service uptake/use ^(32, 130)
SRHR knowledge	SRHR knowledge ^(123, 131)
Violence and safety	Violence and safety ^(124, 125)
Gender norms	Gender norms ^(48, 132)
Agency	Agency ^(66, 133)
Mental health	Mental health ⁽¹²⁶⁾
	Intervention acceptability ⁽¹²⁹⁾
	Satisfaction with intervention/services ⁽¹²⁸⁾
	Feasibility ⁽¹²⁸⁾

Intervention Power Calculation and Sample Size Considerations: Power calculations and sample size for the adolescent health club component are determined based on the SRH knowledge measure.⁽¹²³⁾ With 85% power, in a two-arm comparison design (similar to round one in Figure 2 above), and based on data from a previous intervention study⁽¹³¹⁾ in which the investigators found a pre/post intervention difference of 1.3 and a standard deviation of 3, we will need 50 pairs or 100 participants in the adolescent clubs total. Broken into four groups, I plan for each group to be 25 participants. As this calculation does not take into consideration within-group analysis, it is a ≈20% overestimate, which allows for 20% loss to follow-up, or participant drop-out without loss of statistical power. However, to minimize bias, I am targeting 95% follow-up. 95% follow-up is based on our team's procedures for tracking and retaining adolescent health club participants. Specifically, we will make clear the participation expectations upon recruitment, consent, and the initial health club meeting. We will follow-up with participants who miss club sessions via cell phone and home visits as needed. These methods have been used by the research team in previous studies in the study area.

Implementation and Intervention Data Analysis

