For the provider/staff sensitization component, a total of N=60 providers and staff will be recruited from the public and private clinics where AGYW were recruited for the formative quantitative survey. There will be two separate groups of 20 people each who undergo the sensitization workshop. The workshop will take place over four days. In previous work in the study area, retaining providers for a short intervention such as the one described in this proposal has not been a challenge and therefore we anticipate no challenges in recruiting the required sample size.

For the adolescent health club component, households with AGYW between the ages of 15 and 25 will be identified by Apnalaya's field team from randomly selected block sectors of the study area. AGYW and their mothers (if unmarried and under the age of 18) will be approached by a member of the research team and the adolescent health club intervention will be explained. If consent is obtained, the AGYW will be enrolled to either participate in the health club immediately or join the wait-list. An initial sample of 50 AGYW will be recruited (one group of 25 to begin intervention immediately, and one wait-list group). After the first intervention group has completed the health club curriculum, the wait-listed group will begin the intervention, and another 25 AGYW will be recruited for a wait-list. This will continue until four groups of 20-25 AGYW complete the health club intervention. Factoring in an attrition rate of 20%, the expected N at endpoint is 80. AGYW will complete the pre-intervention evaluation instrument upon enrollment. When young women complete the health club curriculum, they will also complete the post-intervention evaluation instrument. A sub-sample of young women will be asked

to participate in a focus group discussion to reflect on the club's impact and acceptability. To limit differences in

the time needed to assemble the health club groups, we will avoid recruiting during busy religious festivals/holidays (such as Ramadan) or vacation periods.

b. Describe how potential subjects are contacted.

Key informants and healthcare providers/staff for all phases will be contacted in the following ways: through in-person meetings, and snowball referrals/introductions via email (email recruitment template is attached) or cell phone.

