AGYW for the qualitative data collection will be contacted primarily through Apnalaya's outreach activities, and through snowball referrals/introductions either in person or through cell phone. For the quantitative portion of the formative research, a random sample of adolescent girls and young women (AGYW; ages 15-25 years old) seeking care at a set of public (N=3) and private (N=3) healthcare facilities in the study area will be referred by their healthcare provider/Apnalaya health promotion team member to me or my research assistant and asked to participate in a brief survey.

For the adolescent health club component, households with AGYW between the ages of 15 and 25 will be identified by Apnalaya's field team from randomly selected block sectors of the study area. AGYW and their mothers (if unmarried and under the age of 18) will be approached by a member of the research team and the adolescent health club intervention will be explained. If consent is obtained, the AGYW will be enrolled to either participate in the health club immediately or join the wait-list.

c. Who is recruiting potential subjects?

Subjects will be recruited by the 3-4 members of Apnalaya's adolescent outreach team.

4. Assessment of Current Health Provider Relationship for HIPAA Consideration:

Does the Investigator or any member of the research team have a direct existing clinical relationship with any potential subject?

Yes, all subjects

Yes, some of the subjects

No

If yes, describe the nature of this relationship.

None of the members of the research team will have a direct existing clinical relationship with any potential subjects, however, healthcare providers and Apnalaya staff may tell potential subjects about the study, and refer them to me or my research assistant.

5. Request for waiver of HIPAA authorization: (When requesting a waiver of HIPAA Authorization for either the entire study, or for recruitment purposes only. Note: if you are collecting PHI as part of a phone or email screen, you must request a HIPAA waiver for recruitment purposes.)

Choose one:

For entire study

For recruitment/screening purposes only

For inclusion of non-English speaking subject if short form is being used and there is no translated HIPAA research authorization form available on the University's HIPAA website at hipaa.yale.edu.

i. Describe why it would be impracticable to obtain the subject's authorization for use/disclosure of this data: *Write here*

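### Round-one women appear to be randomised at consent into two fixed groups of 25, so a small field team in an open trial could partly foresee assignments before choosing whom to approach

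*Combined protocol and SAP*

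**What the plan says.** Section I, 4 (Adolescent Health Club Component and Evaluation) links allocation to consent: "If consent is obtained, the AGYW will be enrolled, and randomized to either participate or join the wait-list". Section III, 3a and 3b give the same sequence without mentioning randomisation: "If consent is obtained, the AGYW will be enrolled to either participate in the health club immediately or join the wait-list".

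The round-one total is fixed in Section III, 3a: "An initial sample of 50 AGYW will be recruited (one group of 25 to begin intervention immediately, and one wait-list group". The power text in Section I, 4 agrees: "Broken into four groups, I plan for each group to be 25 participants". Section III, 3a is looser elsewhere: "This will continue until four groups of 20-25 AGYW complete the health club intervention". After round one there is only one destination for new recruits: "the wait-listed group will begin the intervention, and another 25 AGYW will be recruited for a wait-list".

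Section III, 3c states: "Subjects will be recruited by the 3-4 members of Apnalaya's adolescent outreach team". Under Section III, 6, the field worker who recruits also starts the consent process, and the investigator and research assistant then re-affirm it. Random selection applies to block sectors. No list or order of approach is given for women within a sector. The same Section I paragraph also places clubs in different sectors to limit contamination.

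The documents give no method of generating the sequence, no concealment, no custodian of the list, and no statement that the draw waits until recruitment closes.

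**The concern.** The arm is obvious once assigned, because a woman either starts the club or waits. When two groups of known size are filled as women consent, anyone who counts past assignments knows how many places remain in each. Hiding the list does not prevent this, since the information comes from the visible assignments and the known total. Doing the baseline survey before each allocation does not prevent it either, because the recruiter can form the guess before choosing whom to approach.

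Round one is the only round with two possible destinations, so it is the only round in which randomisation can protect a treated-versus-untreated comparison. The Quantitative analysis text plans the group 1 v group 2 comparison, and the power text likens its two-arm design to round one. There are also ordinary reasons to care which slot is open: the wait lasts about 2.5 months, attendance is paid per session, and the team targets 95% follow-up. If women who are keener or freer to attend were approached when a club place was likely, the comparison would carry selection bias.

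**Working it through.** **Inputs.** Group size n = 25, total 50 (Section III, 3a; Section I, 4 power text). Planned difference 1.3, SD 3 (same power text). No allocation mechanism is stated, so two are examined. In both, the guesser keeps a count and names the group with more places left.

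**The plan's own figure.** The plan gives no figure for predictability. Its sample size reproduces on a paired reading: ((1.960 + 1.036) × 3 / 1.3)² = 47.8, and the exact paired t-test with 50 pairs has 85.2% power (two-sided alpha of 0.05 assumed; none is stated). The 1.3 and 3 are used below only as a yardstick.

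**Random ordering of 25 + 25.**
- 4^25 / C(50,25) = 1.126×10^15 / 1.264×10^14 = 8.907.
- Expected correct guesses = n + (4^n / C(2n,n) − 1)/2 = 25 + 7.907/2 = 28.95 of 50, or 57.9%.
- Expected assignments known outright = 2n/(n+1) = 50/26 = 1.92. The last is always known; at least the last two with probability 0.49; at least the last three with probability 0.235.
- Chance of a correct guess by position: 50% for the 1st woman, 54.5% for the 20th, 61% for the 40th, 68% for the 46th, 74.5% for the 48th, 100% for the 50th.

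**Coin tosses until one group is full.**
- Expected assignments known outright = 2n × C(2n,n) / 4^n = 50/8.907 = 5.61. At least two are known with probability 0.885, at least ten with probability 0.154.
- Expected correct guesses = (50 − 5.61)/2 + 5.61 = 27.81 of 50, or 55.6%. Nothing is predictable before one group fills.

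**Groups of 20 + 20, random ordering.** 23.49 of 40 correct (58.7%), and 1.90 known outright on average.

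**Illustrative shift in the group 1 v 2 difference.** The women whose slots are known all fall in one group of 25. If each is steered in the club's favour by d SDs, the unadjusted shift is (number known / 25) × d × 3.

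| Mechanism | d = 0.5 | d = 1 | Share of 1.3 |
|---|---|---|---|
| Random ordering (1.92 known) | 0.12 | 0.23 | 9% to 18% |
| Coin toss until full (5.61 known) | 0.34 | 0.67 | 26% to 52% |

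This counts only slots known for certain, and not any steering on a merely probable guess.

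**One batch draw after 50 consents and baselines.** Correct guesses at the time of approach are 50%, and none are known in advance. The sample size does not change.

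**The case against.** The strongest reply is that allocation of women one at a time is inferred. The text says a consenting woman is enrolled and randomised; it does not say she is randomised on the spot, and recruiting an initial sample of 50 fits a single draw. That stands as a limit. It does not dispose of the point, because no section describes such a draw and the ordinary reading of the sentence is allocation at consent.

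Second, what the recruiters know is partly inferred. The Research Plan has community health workers identify households and a research team member approach women, and nothing says who assigns or whether recruiters see a tally. This also stands, although a team of 3-4 in an open trial needs no formal tally.

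Third, the 20-25 range for group size makes the end point less certain. That weakens certainty about the last slots, but hardly changes the guessing rate (58.7% for groups of 20).

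Fourth, the pre-intervention survey records demographics and knowledge, and the primary analysis is a repeated-measures mixed model. Steering on measured characteristics would be visible and partly adjustable. Differences in motivation or freedom to attend would not be.

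Fifth, this is a pilot whose hypotheses concern pre/post change, and the group 1 v 2 comparison is one of several. That limits the importance of the point, but the fix is cheap.

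**Conclusion.** The point holds on the ordinary reading of the allocation sentence, and its size is modest: 28.95 or 27.81 correct guesses in 50 against 25 by chance, with a mean of 1.9 or 5.6 assignments known outright depending on the mechanism. The plan should state when the draw is made and who makes it.

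A reader might infer three stronger things that the documents do not support:

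- **That staff become steadily more certain and always know the last several assignments.** Under coin tossing nothing is predictable until one group fills. Under a random ordering only the final assignment is always known.
- **That the group 1 v 2 comparison is biased by a quarter to a half of the planned effect.** That range belongs to the coin-toss case with every known-slot woman steered by 0.5 to 1 SD. The random ordering gives 9% to 18% on the same assumption, which the documents neither support nor exclude.
- **That no analysis could help.** Baseline adjustment could remove part of any shift, but not the unmeasured part.

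One unresolved passage could make matters worse. If placing clubs in different sectors means that groups are formed by sector, assignment is known before any woman is approached, and the sequential arithmetic above no longer applies.

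**What to change.** In Section I, 4 (Adolescent Health Club Component and Evaluation) and Section III, 3a and 3b, replace allocation at consent with this order:

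1. Recruit and consent all round-one women and complete their pre-intervention surveys.
2. Close the list of study IDs.
3. Have a team member who does not recruit draw the immediate and wait-list groups in one batch. The plan already uses R, so a short script suffices.
4. Release all assignments together, and state that no one is added or moved afterwards.

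Reconcile this with the placement of clubs in different sectors. State whether women or sectors are randomised, and make the draw for that unit only after the list is closed.

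If women are the unit, the cost is protocol wording and a short script, since Section III already assembles an initial 50. The earliest recruits would wait until the list is complete to learn their group. Settling the sector question is a design decision and may need more than wording.

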Study Design: Neither providers/staff or clinics can be randomized, as only a subset of the clinics/providers in the study area see enough AGYW to meet inclusion criteria, and some providers/staff who participate will work in the same clinics. Providers/staff will complete brief pre- and post-training surveys; however, the primary measures of their intervention will be derived from the AGYW’s outcomes.

For the adolescent health club component, the pilot study employs a waitlisted control group design^(117, 118) (Figure 2). In this modified version of the stepped wedge design,⁽¹¹⁹⁾ all groups receive the intervention, and participants serve as their own controls. This design utilizes a smaller sample size of AGYW and fewer facilitators, making it more feasible for a K award, while still enabling all participants to participate in the intervention. The waitlisted control design also avoids some of the

[figure not shown]

Figure 2: Wait-list design for four adolescent health club groups.

challenges associated with carryover effect that can occur in other crossover designs, as participants move unidirectionally from control to intervention.^(117, 118, 120) The adolescent health club curriculum (which takes approximately 2.5 months to complete) will be sequentially administered to four groups, each with a waitlisted control group. Individuals can be compared to themselves, and the other groups. Sequentially administering the intervention will be more feasible than administering the intervention simultaneously to separate neighborhood clusters, limiting the number of facilitators needed.

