Qualitative analysis: The observations and interviews conducted during and after the intervention will be transcribed, translated into English (as needed), and entered into the qualitative software analysis program Atlas.ti (v.8.1).⁽¹¹²⁾ A modified framework approach^(113, 115, 134) to coding will be used in which deductive themes will be developed *a priori* based on the study's conceptual framework and implementation indicators, and inductive codes will be developed and applied iteratively based on review of the transcribed documents. Text will then be reviewed for patterns of consistency, variation, relationships between themes and exemplary cases or quotations. Qualitative data will also be merged with the quantitative findings to triangulate results and further contextualize the quantitative indicators, in keeping with a parallel mixed methods design.^(114, 116, 135)

Quantitative analysis: I will use R to analyze the data. Descriptive statistics will be obtained for continuous and categorical variables. The health outcome scales to be used in this study are well-validated (in contrast to the implementation outcome scales), and can be assumed to have approximate normal distributions, although these assumptions will be checked. This study will conduct both within and between-group analyses for the adolescent club component. All subjects will have pre- and post-treatment within-subject measures, and these comparisons can be preliminarily analyzed with paired t-tests. Primary analyses will focus on using repeated measures general linear mixed models to examine comparisons across recruitment cohorts. We will also be able to compare the treated participants from group 1 with the untreated participants in group 2, followed by the group 2 treated participants with the untreated group 3 participants, and finally the group 3 treated participants with the untreated group 4 participants, and can use repeated general linear mixed models for this unbalanced design.

5. Genetic Testing N/A

A. Describe

- i. the types of future research to be conducted using the materials, specifying if immortalization of cell lines, whole exome or genome sequencing, genome wide association studies, or animal studies are planned *Write here*
- ii. the plan for the collection of material or the conditions under which material will be received *Write here*
- iii. the types of information about the donor/individual contributors that will be entered into a database *Write here*

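### The plan's 85% power is labelled a two-arm comparison, but its inputs give about 57% (50 v 50) or 32% (25 v 25) for an unadjusted two-arm test

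*Combined protocol and SAP*

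**What the plan says.** The calculation appears twice in Section I of the combined protocol and SAP: in item 4 (Intervention Power Calculation and Sample Size Considerations) and, slightly shortened, in item 13 (Statistical Considerations). Item 4 ties the figure to a particular contrast: "With 85% power, in a two-arm comparison design (similar to round one in Figure 2 above". Both places then give the inputs and the result, a "difference of 1.3 and a standard deviation of 3, we will need 50 pairs or 100 participants in the adolescent clubs total", to be split into four groups of 25. Both say that within-group analysis was left out of the calculation. Item 4 concludes that the number is therefore about 20% too large, "which allows for 20% loss to follow-up, or participant drop-out without loss of statistical power". Item 13 says only that it is slightly too large and leaves some room for attrition. Neither place states alpha, sidedness, the test used, or whether the SD of 3 is of scores or of change.

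On design, the club curriculum "will be sequentially administered to four groups, each with a waitlisted control group". Section III, item 3a (Recruitment Procedures) sets round one at 25 women starting at once and 25 wait-listed, and expects 80 women at endpoint after 20% attrition.

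On analysis, item 4 (Quantitative analysis) says of the pre/post data that "these comparisons can be preliminarily analyzed with paired t-tests". It then says: "Primary analyses will focus on using repeated measures general linear mixed models to examine comparisons across recruitment cohorts". The contrasts between consecutive groups come last: "We will also be able to compare the treated participants from group 1 with the untreated participants in group 2", and so on down to group 4.

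**The concern.** The 85% is the only power figure in the plan, and it carries a two-arm label with a pointer to round one. A reader will take it as the power of the contrast between treated and wait-listed women. Yet pairs belong to a paired test, and an unmatched two-arm test with the same difference and SD needs roughly twice as many women in each arm as a paired test needs pairs.

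If the label is wrong, a null result for treated against wait-listed women could be read as evidence of no effect when the comparison had little chance of showing one. That matters in a pilot whose Aim 3 is meant to inform later research. The reassurance about drop-out rests on the same calculation.

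**Working it through.** **Inputs.** Difference 1.3, SD 3, target power 85%, 50 pairs or 100 participants (items 4 and 13); 25 v 25 in round one and 20% attrition (Section III, item 3a). Alpha is not stated; two-sided 0.05 is assumed, with one-sided 0.05 shown as well. Standardised difference d = 1.3/3 = 0.433.

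**Step 1: reproduce the plan's 50.** For a paired test the normal approximation is n = [(1.960 + 1.036) × 3/1.3]² = 47.8. The exact calculation (noncentral t) gives 49.8, so 50 pairs, with 85.2% power at 50. The stated number is matched, provided SD 3 is the SD of the within-pair difference.

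**Step 2: try the comparison the plan names.** For two independent arms, n per arm = 2 × 47.8 = 95.6 by the normal approximation. The t-test gives 96.6, so 97 per arm or 194 in all. One-sided 0.05 needs 77.3, so 78 per arm. Neither gives 50 per arm.

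**Step 3: power of the unadjusted two-arm t-test at the available sizes.** Noncentrality is d × √(n/2), with 2n − 2 degrees of freedom.

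| Women per arm | Noncentrality | Power, two-sided 0.05 | Power, one-sided 0.05 | Difference detectable with 85% power (two-sided) |
|---|---|---|---|---|
| 50 (all 100 women, notional) | 2.17 | 57% | 69% | 1.8 |
| 25 (round one) | 1.53 | 32% | 45% | 2.6 |
| 40 (50 less 20%) | 1.94 | 48% | 61% | 2.0 |
| 20 (25 less 20%) | 1.37 | 27% | 38% | 2.9 |

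By the normal approximation, 50 v 50 would need a two-sided alpha of about 0.26 to reach 85%. At 25 v 25 the detectable difference is twice the assumed one (2.6/1.3 = 2.0).

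**Step 4: what could the pairs be?**
- Treated and wait-listed women paired with each other: 50 pairs would then be 100 participants, but no matching is described anywhere.
- Pre/post pairs: each woman is her own pair, so 50 pairs are 50 women. The calculation would also be a within-group one, which both sections say was left out.

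Neither reading agrees with the whole text.

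**Step 5: the attrition statement.** For the two-arm comparison, 20% loss lowers power from 57% to 48% (50 to 40 per arm) or from 32% to 27% (25 to 20 per arm). For 50 pairs cut to 40, power is 76% two-sided, so the statement fails; at one-sided 0.05 it is 85% (39.7 pairs needed), so it holds. If all 100 women are counted as pre/post pairs, power is about 99% at N = 100 and 97% at N = 80. Those two figures are two-sided and require that SD 3 is the SD of change and that outcomes do not cluster by club. The documents give neither, and the clubs are geographically separate: "Clubs will be conducted in separate neighborhood sectors, to limit contamination".

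**The case against.** Four points can be made for the plan.

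- **The design does not rest on 25 v 25.** Women serve as their own controls, the mixed model is primary, and the group-by-group contrasts are introduced as something that can also be done. One hundred untreated and 100 treated measurements, with SD 3 in each and no correlation within women, would give about 86%. This stands as a reason not to call 32% the power of the study. But it describes a before/after comparison, not the two-arm comparison to which the plan attaches its figure.
- **A one-sided test could explain the attrition allowance.** Aim 3 predicts improvement, 40 pairs suffice one-sided, and 40/0.8 = 50 fits the 20% margin in item 4. That is possible, since sidedness is not stated, so the criticism of 40 pairs holds only for a two-sided test. It does not help the two-arm label, where one-sided power is 69% and 45%.
- **The paired origin is inferred.** This is correct. No formula is named, and the inference conflicts with the remark about within-group analysis and with counting 50 pairs as 100 women. The shortfall in Step 3 does not depend on where the 50 came from.
- **Baseline adjustment or a mixed model may do better than an unadjusted test.** It may, so the figures above are limited to unadjusted comparisons. The plan gives no within-person correlation. Its text describes one survey at enrolment and one on completing the curriculum, so it does not establish that wait-listed women have two untreated measurements. Clustering within clubs would work in the opposite direction.

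**Conclusion.** The 85% is wrong for the comparison it is attached to. At two-sided 0.05 (assumed), the plan's inputs give about 57% for an unadjusted 50 v 50 and 32% for the 25 v 25 of round one, against 97 per arm needed for 85%. One-sided 0.05 does not close the gap. The statement that 20% loss costs no power is wrong for the two-arm comparison and, for 50 pairs cut to 40, true only one-sided.

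A reader might go further and infer that the trial is underpowered, that it should enrol 194 women, or that the Aim 3 hypothesis will probably fail. The documents do not support this. Aim 3 is a pre/post hypothesis, for which 100 women may be ample. The power of the primary mixed model is not stated and cannot be computed without a within-person correlation and a club intraclass correlation. Nor can it be taken as established that the authors ran a pre/post paired calculation. This is an error of labelling and reporting that should be fixed, and it does not call for a redesign.

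**What to change.** In Section I, items 4 and 13:

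1. Stop attributing 85% to the two-arm or round-one comparison. State the test, alpha, sidedness and type of SD actually used, and reconcile 50 pairs with 100 participants. The authors should supply the derivation; it should not be guessed for them.
2. Give the unadjusted two-arm power as about 57% for a notional 50 v 50 and 32% for 25 v 25, with a detectable difference of about 2.6 at 85% power for 25 v 25, all at two-sided 0.05.
3. Remove the claim of no lost power under 20% attrition for the two-arm comparison. If the pre/post comparison is meant, say so and give about 99% at N = 100 and 97% at N = 80, as conditional on SD 3 being the SD of change and on no clustering by club.
4. Give the power of the primary mixed model, with the within-person correlation and club intraclass correlation assumed for it.

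The cost is rewording in two places and one further power calculation. No participants are added and no analysis changes. The drawback is that the stated power for the controlled comparison becomes less favourable.
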